1.2.2 Practical significance

This study aims at demonstrating the effectiveness of IMR on the illness management skills and recovery of the patients.

The added value for participants on different areas of life is examined. The research can contribute to answering the question whether IMR should be a recommended intervention.

Research can point to types of patients for whom IMR could be effective and conditions for success.

1.2.3 Scientific significance

The research may contribute to answering the question whether IMR can be called an EBP. In the RCT by Hasson-Ohayon et al. (2007) IMR participants showed significant improvements in knowledge about their illness and showed progress towards their personal goals compared to patients with care as usual (CAU). Scores of clinicians showed a significant improvement in 'overall outcome'. Both the IMR- as the CAU group showed a significant improvement in coping and neither group showed change in social support.

In the RCT by Levitt et al (2009), executed in supported housing the intervention group scored significantly better in illness management and clearly had fewer symptoms and better psychosocial functioning.

In the RCT by Färdig et al (2011), the IMR-participants showed better illness management, less symptoms, better psychosocial functioning.

An effective factor in IMR in groups could be peer support (see Castelein et al, 2008a and 2008b and Castelein 2009), for which also indications come forward in our pilot study.

Nevertheless, in the field of psychiatric research in the Netherlands there still are doubts about the evidence-based status of IMR. There has not yet been done a RCT on IMR in the Netherlands. IMR is not yet mentioned in the multidisciplinary guidelines on Schizophrenia in the Netherlands (see 1.1).

Transfer of knowledge

IMR and the scientific status of IMR have a growing interest in the Netherlands and abroad. The results of the study are thus of significance for many people and will be studied by many. The results of our study will be transferred by newsletters, conferences and articles in scientific journals.

2. Objective

The aim of this study is to examine the effectiveness of the IMR program compared to care as usual (CAU) in patients with SMI.

3. Research questions

Research questions are:

What are the effects of "IMR + CAU", compared to "CAU only" on:

- 1. Illness management, as experienced by clients (primary outcome measure)
- 2. Recovery.

The hypotheses are that "IMR + CAU", (IMR offered in group format), compared to "CAU only" leads to:

1. Better Illness Management:

(Better scores on IMR-scales, less symptoms and relapses, better medication adherence, less alcohol & drugs use, more insight into their own problems, more social and coping skills, more social support).

2. Better recovery:

(Better general recovery, less self-perceived stigma, more self-esteem, achievement of more meaningful goals, more quality of life, more satisfaction, and better social functioning).

3. Improved cost-effectiveness.

4. Design

The design is a randomized controlled trial in which patients are assigned to the experimental condition (IMR) or the control group, after providing written informed consent:

- Group 1. IMR program, offered in a group format + care-as-usual (CAU).
- Group 2. Care-as-usual (CAU)

At randomization, we apply the 'minimization method' (Beller et al 2002). This is a dynamic random allocation method, with the ability to stratify on variables that the outcomes (possibly) influence. We stratify on diagnosis (psychotic disorder yes or no).

The procedure is performed using www.randomizer.org. Using the block-design we ensure that patients end up in the desired ratios in the two conditions (IMR group + CAU vs. CAU).

We have planned three moments of measurement. These moments are

- 1. prior to the randomization
- after the training (in the experimental condition this time may vary depending on the duration of the group, the mean duration of the training in the pilot study was 12.6 months).
 The final (second) moment of measurement for the control group is 12 months after the first moment of measurement.
- 3. The follow-up measurement is 6 months after the second measurement.

5. Study population

5.1 Patients

Inclusion criteria are:

- Patients with serious and persistent psychiatric illnesses. Most of them will be patients who have a psychotic disorder, schizoaffective disorders or bipolar disorders with or without comorbid disorders (such as substance abuse and personality disorders)
- The patient is treated on an outpatient basis
- Written informed consent .

5.2 Exclusion criteria

Exclusion criteria are:

- Having done an IMR-training
- Organic brain syndrome.
- Incompetence regarding the giving of informed consent.
- Patients with severe cognitive impairments who are unable to follow the training
- Insufficient knowledge of the Dutch language (so that they cannot participate in the group).

5.3 Sample Size

Based on the effect sizes of the studies of Hasson et al. (2007) with 210 participants (.41, Cohen's d), Levitt et al. (2009) with 104 participants (.36) and Färdig et al. (2011) with 41 participants (.60) we expect a medium effect size of 0.40.

Based on the power analyses with three moments of measurement (mixed models) and equal allocation to experimental and control group, a power of .80, correlation between measures .50, alpha at 0.05 and an effect size of .40, we need to randomize 148 patients, 74 to the experimental condition and 74 to the CAU-group (see Twisk (2003) and Guanghan L. and Kung-Yee L. (1997).

Because of the (conservatively estimated) expected drop-out from treatment in the experimental condition of 50% we choose to allocate more patients to the experimental (IMR-) condition than to the CAU-group (proportions of 3:2). Then we need to randomize 185 patients, 111 patients to the experimental condition and 74 to the CAU-group.

Because we expect a total drop-out in each group from measurements of 8 % we need 80 patients in the control condition and 120 patients in the experimental condition. In total: 200 patients (see Annex 1).

6. Intervention

The average duration of the total IMR-training is 12 months. The IMR-training consists of 11 modules that are given weekly. The first module is given individually. During this individual module the patients decide which goals they want to work on during the program.

Then the patients join an IMR group for the other modules. Each module takes about 3 to 4 sessions of one and a half hours each. The IMR group is guided by two trainers (psychiatric nurses). The trainers received a two-day course in IMR and attend supervision once every two weeks.

The modules are described in the IMR-workbooks, translated into Dutch, which the patients received. If necessary, the original American text is adapted to the Dutch context. The modules are: 1. Recovery Strategies, 2. Practical Facts about Mental Illness, 3. Stress-Vulnerability Model, 4. Building Social Support, 5. Using Medication Effectively, 6. Alcohol and Drugs Use, 7. Reducing Relapses, 8. Coping with Stress, 9. Coping with Problems and Persistent Symptoms, 10. Getting Your Needs Met in the Mental Health System, 11. Health for you.

The trainers use techniques from motivational interviewing, psychoeducation and cognitive-behavioral therapy (CBT). Peer group support is part of the IMR-training. Home assignments are provided. Workbooks and homeassignments can be accessed via the internet. There is feedback on homework from trainers on the Internet. A patient is considered to be a "completer" of the IMR-training if he has completed at least 70% of the sessions.

The quality of the implementation of the intervention is checked in two ways:

1. Degree of fidelity of the implementation of IMR. (Quality of implementation).

To measure whether the program is implemented according to the original intent, the researchers determine the model fidelity using the IMR fidelity scale (Mueser et al. 2002b).

A translation of this scale has been made and training in the use of the IMR fidelity scale has been followed in collaboration with [name], Ph.D. and A. [name] of UIPUI, University of Indianapolis USA, together with Saxion Academy Deventer.

2. Quality of the trainers.

To be able to measure this, we will use a scale recently developed by UIPUI in Indianapolis USA: the Illness Management and Recovery Treatment Integrity Scale (IT IS). This scale rates the quality of the trainers with respect to having experience in guiding groups, (social) skills training, ability to structure role playing and to integrate text of the workbooks with personal goals and problems of a participant, and maintenance of a positive attitude. Publications are submitted.

7. Intervention- and control group

Group 1. Experimental condition

These patients participate in the IMR-training as well as CAU.

Group 2. Control Condition

These patients only get CAU. This consists of regular individual meetings (usually every two weeks) with a community psychiatric nurse (in Dutch: SPV). The topics are related to symptoms and handicaps related to the illness and methods for managing them. The applied methods include eg supportive therapy, CBT or help in finding (volunteer) work.

If CBT is indicated it can be given by a psychologist or a behavior therapy assistant. The SPV may also help to solve practical problems such as finding housing or the cleaning up of debts. At least once a year, the patient has an appointment with a psychiatrist for the optimization of medication and a somatic examination.

The difference between the two conditions is that the patient in the 'IMR + CAU' condition follows a structured IMR-training, aimed at achieving their own goals and learning of 'illness management'. We expect that patients less systematically work on their personal goals during 'CAU only' and learn less about illness management. To control for type of interventions in CAU, all interventions will be registered.

8 Methods

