8.2 Procedures

8.2.1 Selection of patients

It is assumed that we need to screen approximately 687 patients for participation in the study. An estimated 515 patients (80%) will meet all inclusion criteria and will be asked by the clinicians to participate in the study. It is expected that about 40% of these patients are willing to participate in the study and then we get the amount we need (n = 200). Patients will be randomized in a ratio of 3:2. After drawing lots there will be 120 patients in the IMR-condition and 80 in the control condition.

We expect that in the IMR condition 37% will drop-out of IMR in the phase between randomisation and the inflow into the (individual) Module 1 and in the phase from module 1 to the inflow in the IMR group (module 2). We expect that in the IMR-condition there will approximately 78 patients who start the IMR- training groups. Based on the results of the pilot study it is expected that 77 % (n = 60) of these people will complete the IMR groups.

Drop out of the IMR-program does not mean dropping out of the study (see in 8.2.4 the intention-to-treat principle). We expect that of the 120 patients in the experimental condition, that in the second moment of measurement score at least 115 patients can be measured, and at follow-up measurements at least 111 patients. We expect that of the 80 patients in the control condition that in the second moment of measurement score at least 77 patients can be measured and at follow-up measurements at least 74 patients (See Annex 1, flowchart of randomisation). We expect this dropout of the study is only 8% because patients who want to withdraw from care will not wish to participate in IMR.

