8.2.4. Research data

Data on primary, secondary and tertiary outcome measures and the mediating factors will be collected at baseline (before randomization), after the IMR-training (from 9 to 12 months) and during follow-up (after 15 - 18 months). The interviewers will be blind for the (experimental or control) condition of the patient. For the recruitment of participants and data collection, students will be employed.

During the first contact (at baseline) and after the patient has given informed consent, the research interview will take place and the interviews will be conducted. Subsequently randomization will take place. Each assessment will last up to 80 minutes. If desired, the interview will take place on two occasions. The assessments will be done at the location where the patient usually comes. Besides the previously mentioned outcome measures and mediating factors at baseline the following data will also be collected:

- Demographic data: age, sex, living situation, source of income, education level, country of birth of the patient and of his father and his mother.

- Consumption of mental health care: number of outpatient contacts, number of crisis contacts, number of admissions and the number of compulsory admission orders (total and in the last two years) during the past two years before and after moment of measurement 1.
- Psychiatric diagnosis: DSM-IV-TR diagnosis (five axes) according to the clinician. We realize that this is not always reliable, but it is not possible with the resources available to do a standardized diagnostic interview.

The analysis will be based on the intention to treat principle. Data will be collected of patients who drop out of the IMR program. Based on the pilot study, during the IMR intervention, 50 % drop out from IMR is expected. In order to do analyses related to generalizability of the study, the demographic characteristics of all patients who refused to participate will be registered, as well as the characteristics of the patients who drop-out from the study.

The demographic variables, consumption of mental health care and psychiatric illness will be collected by the researcher from the administration of the institution, supplemented by data from the file.

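### Raising the IMR arm from 74 to 111 does not compensate for 50% treatment drop-out under intention to treat, so power of .80 holds only for some readings of the effect size 0.40

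*Protocol*

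**What the plan says.** Section 5.3 expects an effect size of 0.40, based on three earlier trials (0.41, 0.36 and 0.60). The base calculation assumes "a power of .80, correlation between measures .50, alpha at 0.05 and an effect size of .40", with three measurements and equal allocation, and concludes "we need to randomize 148 patients, 74 to the experimental condition and 74 to the CAU-group".

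The next step changes the allocation to 3:2 and gives one reason: "Because of the (conservatively estimated) expected drop-out from treatment in the experimental condition of 50% we choose to allocate more patients". The result is "Then we need to randomize 185 patients, 111 patients to the experimental condition and 74 to the CAU-group". A further 8% for missed measurements brings the total to 120 + 80 = 200.

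On the analysis, section 8.2.4 states: "The analysis will be based on the intention to treat principle". Section 8.2.1 adds that leaving the IMR programme is not leaving the study, and expects 111 of 120 IMR patients and 74 of 80 controls to be measured at follow-up. On uptake, it expects 78 of the 120 to start a group, and of those "it is expected that 77 % (n = 60) of these people will complete the IMR groups". Section 9 compares the groups at the final and follow-up assessments with control for baseline.

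**The concern.** Section 5.3 treats treatment drop-out as a loss of numbers to be made up by recruiting more IMR patients. Under intention to treat no numbers are lost. The drop-outs are measured and analysed in the IMR arm, and whatever benefit they miss lowers that arm's mean. The quantity to adjust is the effect size, and section 5.3 leaves it at 0.40 throughout.

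At stake is how the primary result would be read. If 0.40 is an effect in patients who receive IMR, the true intention-to-treat power could be well below .80, and a null result could be taken as adequately powered evidence against IMR.

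**Working it through.** **Inputs.** From section 5.3: d = 0.40, correlation 0.50, alpha 0.05, power .80, 74 per arm, then 111 + 74, and 50% treatment drop-out. From section 8.2.1: 78 group starters and 60 completers of 120. From the drop-out paragraph of section 1.2.1: drop-out of 29% overall in one earlier trial and 19% in the intervention group of another. Two-sided testing is an assumption; of the forms tried, the one-sided versions give at most 78 and none gives 74.

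**Reproducing 74.** n per arm = 2(1.96 + 0.842)² × v / d². With v = (1 + 0.5)/2 = 0.75 this is 2 × 7.85 × 0.75 / 0.16 = 73.6, so 74. The same v = 0.75 arises from two averaged post-baseline measurements without baseline adjustment, or from one follow-up adjusted for baseline (1 − 0.5²). The protocol does not say which was used.

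**The step to 111.** 74 × 1.5 = 111, which is simply the 3:2 ratio. Completers: 111 × 0.5 = 55.5, about 56. Keeping 74 completers would take 74 / 0.5 = 148. A comparison of 56 completers with 74 controls at d = 0.40 has power 0.74, and 60 completers give 0.76.

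**Intention-to-treat power, 111 v 74.** Power = Φ(d / √[v(1/111 + 1/74)] − 1.96). The standard error is 0.130 for v = 0.75 and 0.106 for v = 0.50. The second is the baseline-adjusted mean of two follow-ups: (1 + 0.5)/2 − 0.5² = 0.50.

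| Average d | Benefit kept by drop-outs, if 0.40 is the effect in those treated | Power, v = 0.75 | Power, v = 0.50 |
|---|---|---|---|
| 0.20 | none | 0.34 | 0.47 |
| 0.25 | 25% | 0.49 | 0.65 |
| 0.30 | 50% | 0.64 | 0.81 |
| 0.35 | 75% | 0.77 | 0.91 |
| 0.40 | all | 0.87 | 0.96 |

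**Effect needed for .80.** 2.802 × 0.130 = 0.364 for v = 0.75, and 2.802 × 0.106 = 0.297 for v = 0.50. With 0.40 as the effect in those treated and 50% drop-out, drop-outs must keep (0.364/0.40 − 0.5)/0.5 = 82% or (0.297/0.40 − 0.5)/0.5 = 49% of the benefit.

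**What the extra 37 patients buy.** At v = 0.75 they lower the detectable effect from 0.40 to 0.364, a margin of about 9%. At d = 0.20, power moves from 0.29 (74 v 74) to 0.34 (111 v 74), and 148 v 74 would reach only 0.37.

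**Other readings of 0.40 (v = 0.75).**
- Full effect in all 78 group starters and none in the rest: 0.40 × 78/120 = 0.26, power 0.52.
- 0.40 already diluted by 19% drop-out, rescaled to 50%: 0.40/0.81 × 0.5 = 0.247, power 0.48.
- 0.40 already diluted by 29%: 0.40/0.71 × 0.5 = 0.282, power 0.58.
- The same 29% dilution, with full effect in all 65% who start a group: 0.40/0.71 × 0.65 = 0.366, power 0.80.
- 0.40 already the intention-to-treat effect at 50% drop-out: at 3:2, 62 controls and 93 IMR patients (155) give .80.

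**Is 50% conservative?** Section 8.2.1 gives 60/120 = 50% completing. Its percentages give 0.63 × 0.77 = 48.5%. Section 8.2.4 calls 50% expected.

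**The case against.** A reader might infer that the trial is underpowered, or that power of .80 is simply false. The documents do not support that. Whether the earlier effect sizes were intention-to-treat or completer estimates lies in sources not at hand, and if 0.40 is the intention-to-treat effect here, power is 0.87. The zero-benefit case is also extreme. Section 6 sets completion at 70% of sessions or more, so a patient who attended 60% counts as a drop-out, and some who left before the groups may have had individual Module 1.

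The variance matters too. Section 9 plans control for baseline, and at v = 0.50 power is 0.81 even if drop-outs keep only half the benefit. That stands, but v = 0.50 would have given 50 per arm, so it is not the basis of the stated 74.

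A reader might also infer that section 5.3 aimed at 74 completers and miscalculated. It names no such target, and 74 × 1.5 follows correctly from 3:2. Nor is 148 the right IMR arm: it would restore a completer count that the primary analysis does not use.

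On the word conservative, other figures point lower. Section 1.2.1 reports 44% drop-out in the pilot, counted from Module 1 only. Section 10 expects 85 patients in groups; 85 × 0.77 is about 65 of 120 completing, or about 45% drop-out. This part of the point is minor.

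What survives is that section 5.3 gives treatment drop-out as its only reason for 185, and that reason does not fit the planned analysis.

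**Conclusion.** The point holds as a fault in the sample-size justification. On none of the main readings is 185 the number needed for .80 because of treatment drop-out. If 0.40 is the effect in treated patients, the number is too small unless drop-outs keep about 82% of the benefit (v = 0.75) or 49% (v = 0.50). If 0.40 is already the intention-to-treat effect, about 155 at 3:2 would do. Only particular combinations, such as the favourable 29% case above, land near .80, and the protocol argues none of them.

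Power of .80 therefore rests on an unstated condition: an average intention-to-treat effect of at least about 0.36 or 0.30, depending on the variance. The figures assume two-sided testing, a correlation of 0.50, a normal approximation, and 111 and 74 patients measured.

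**What to change.** Keep n = 200. In section 5.3:

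- State whether 0.40 is the effect in those treated or the intention-to-treat effect.
- Remove the statement that 3:2 allocation compensates for treatment drop-out. If 3:2 stays, the sponsor should give the actual reason for it.
- Replace the single power of .80 with intention-to-treat power for 111 v 74 over d = 0.20 to 0.40 under the planned model, naming the variance assumed.
- Describe 50% as the expected rate, in line with sections 8.2.1 and 8.2.4.

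The cost is protocol wording and a short table, with no new patients or data. The downside is that the stated power becomes less favourable.

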8.1 Outcome measures

8.1.1 Primary outcome measures

- Illness management and recovery scale-patient self score version

There are two identical IMR-scales (Mueser et al 2004; Salyers et al 2007; Hasson-Ohayon et al. 2008; Dutch translation De Vries 2011) with 15 items completed by patients themselves and by the clinicians, respectively. The patient version of the IMR-scale will be the primary outcome measure.

The consumer and clinician versions of the Illness Management and Recovery (IMR) scales have adequate psychometric properties. These scales have good internal consistency and high 2-week test-retest reliability. Both versions had good convergent validity (Salyers et al. 2007). Factor analysis of both scales showed three similar client and clinician factors: knowledge and goals, coping with illness and a factor that combined effective medication use and reduced alcohol and medication use. These factors explained 40% of the total item variance for the client scale and

47% of the total item variance for the clinician scale. These factors are found to have moderate reliabilities. (Hasson-Ohayon et al. 2007).

The scales have been translated into Dutch and then independently back-translated into English and compared with the original version to identify and correct discrepancies.

8.1.2. Secondary outcome measure

a. Illness management

IMR-scale clinician-rated version will be used to explore effects. This scale is scored by non-blinded clinicians, who are not involved in the IMR-training.

Since the IMR-scales measure multiple dimensions in which each dimension is covered by only one or two questions, some extra questionnaires will be used to further explore & validate the concept of illness management and recovery. These scales are chosen based on the content of the concept of IMR. For this purpose we disentangled the IMR concept into different domains related to illness management and recovery, respectively

Coping: Coping self-efficacy scale (CSES, Chesney et al. 2006) (13-items):

"Exploratory factor analyses (EFA) and confirmatory factor analyses (CFA) revealed a 13-item reduced form of the CSE scale with three factors: Use problem-focused coping (6 items, α = 0.91), stop unpleasant emotions and thoughts (4 items, α = 0.91), and get support from friends and family (3 items, α = 0.80). Internal consistency and test–retest reliability are strong for all three factors. Concurrent validity analyses showed these factors assess self-efficacy for different types of coping. Predictive validity analyses showed that residual change scores in using problem- and emotion focused coping skills were predictive of reduced psychological distress and increased psychological well-being over time". The CSE scale provides according to Chesney et al. a measure of a person's perceived ability to cope effectively with life challenges, as well as a way to assess changes in CSE over time in intervention research.

Social support: Multidimensional Scale of Perceived Social Support MSPSS (Zimet et al.1988) (12 items). The MSPSS was found to have good internal reliability across subject groups. In addition, strong factorial validity was demonstrated, confirming the three-subscale structure of the MSPSS: Family, Friends, and Significant Other. Strong support was also found for the validity of the Family and Significant Other subscales.

Medication compliance: Service Engagement Scale (SES) (14-items)

The Service Engagement Scale (Tait et al. 2002) is a 14-item measure consisting of statements that assess client engagement with services, which case managers rate on a four-point Likert scale from 'not at all or rarely' to 'most of the time'. The total score ranges from a minimum of zero to a maximum of 42. Higher scores indicate lower engagement. Four sub-scales assess availability ('when a visit is arranged, the client is available'), collaboration ('the client actively participates in managing his/her illness'), help-seeking ('The client seeks help to prevent a crisis') and treatment adherence ('The client refuses to cooperate with treatment'). The scale has high internal consistency and retest reliability, including discrimination between criterion groups, in an assertive outreach team (Tait et al, 2002).

Insight into own problems: Insight Scale (IS, 8 self-report items) (PI-scale) (Birchwood et al, 1994). This 8-item self-report scale was designed to be sensitive to changes in levels of insight, and captures three dimensions of insight: perceived need for treatment, awareness of illness and relabeling of symptoms as pathological. Higher scores indicate greater levels of insight. The psychometric properties of the scale are called excellent (Tait et al. 2003).

Symptoms: The Brief Symptom Inventory (BSI) (53 items) (Derogatis & Melisaratos 1983; Derogatis 1993; De Beurs, 2008). The BSI instrument (self-report scale) provides an overview of a patient's symptoms and their intensity at a specific point in time and can be used to measure patient progress during and after treatment to monitor change. The BSI test is brief and requires 8-10 minutes to complete, making it well-suited for repeated administrations over time to evaluate patient progress. The authors report good internal consistency reliability for the nine dimensions , ranging from .71 on Psychoticism to .85 on Depression. Test-retest reliability for the nine symptom mensions ranges from .68 (Somatization) to .91 (Phobic Anxiety), and for the three Global Indices from .87 (PSDI) to .90 (GSI). Studies attesting to the validity of the BSI are found in the manual (Derogatis, 1993).

Relapses: The number of relapses (operationalized in the number of hospital admissions) during and after participating in the IMR-training will be compared with the number of relapses in the year before participating in IMR.

Alcohol & Drugs: One item (item 24) of the Addiction Severity Index (ASI) (McLellan et al, 1980,. Hendriks et al, 1989), asking how much respondents has been bothered the past 30 days by problems with a. alcohol, b. drugs, (a & b separately scored on a 5-point scale).

b. Recovery

The concept of recovery is complex. We choose to assess recovery by using a special scale as well as measuring different aspects of recovery including aspects of what Mueser (see 1.1) calls subjective recovery (self esteem, self stigma, quality of life, satisfaction) and objective recovery (functioning). The outcomes of the intervention on these variables and the association with the outcomes on the primary outcome measure will be tested on an exploratory basis.

- **Recovery**: The Mental Health Recovery Measure (MHRM) (Young & Bullock, 2003), Bullock, 2005); authorized translation in Dutch (Moradi et al, 2007) (30 items).

The MHRM is a 30 item self-report measure designed to assess the recovery process for individuals who have serious and persistent mental illnesses such as recurrent major depression, bipolar disorder, or schizophrenia spectrum disorders. The MHRM is scored using a 5 point Likert Scale (0 to 4) for each item, yielding a theoretical range from 0 – 120 for Total Score. The internal reliability (coefficient alpha) of the MHRM Total Score was .93. One-week test-retest reliability was .92. This scale has three subscales: self-empowerment (13 items), learning & new-potentials (15 items), spirituality (2 items).

According to Mc Cabe et al. (2007) the MHRM assesses three phases of recovery: overcoming sickness; discovering and fostering self-empowerment; and striving to attain overall well-being and reach new potentials.

- **Goals:** Granholm's Goals Template measures progress towards goals on 10 life domains (Employment, Housing, relationships, school, self-care; leisure activities, addictions, money management goal, independence using transportation, general template) and is a method of obtaining objectivation of progress towards personal goals.
- **Self stigma**: The Internal Stigma of Mental Illness (Ismi), 29 items.

This scale is designed to measure the subjective experience of stigma, with subscales measuring Alienation, Stereotype Endorsement, Perceived Discrimination, Social Withdrawal and Stigma Resistance. The ISMI has 29 Likert items. The ISMI has high internal consistency and test–retest reliability. Construct validity and divergent validity was supported by comparisons against scales measuring related constructs with the same methodology. The ISMI has positive correlations with measures of stigma beliefs and depressive symptoms, and negative correlations with measures of self-esteem, empowerment and recovery orientation. Factor analyses of the joint set of items from the ISMI and each scale supported the distinction between constructs (Ritsher 2003).

- Self esteem: The Self-Esteem Rating Scale-Short Form (SERS-SF), 20 items. This scale of 20 items (the original scale has 40 items) has two subscales (positive and negative self-esteem), which is supported by factor analysis. Each subscale ranges from 10 to 70, higher scores indicate higher positive or higher negative self-esteem. This scale has good internal consistency, good test-retest reliability and adequate convergent validity in patients with schizophrenia. (Lecomte et al., 2006).
- **Quality of life:** The EQ-5D (Prieto et al 2003), 5 items. The EQ-5D is the Euro-QOL self-report scale with 5 dimensions and good psychometric properties. According to a Dutch validation study by Lamers et al. (2005), Staring (2010) calculated the items into a weighed total score ranging from -0.33 to 1.00. Higher scores reflect better quality of life.
- **Satisfaction**, Two questions: "Can you tell me how satisfied you are with your life as a whole? and "How satisfied are you with the health care services you visited?" both scored on a 7-point scale. These questions are used in the Routine Outcome Monitoring of the Long Stay sector of Parnassia Bavo Group and is supposed to correlate with all other possible satisfaction-questions which were part of satisfaction questionnaires. (see Delespaul et al. 2006)
- **Social functioning.** The Social Functioning Scale. 7 dimensions (Social withdrawal, relationships, social activities, recreational activities, independence (completence), independence (performance), employment.19 items and 4 checklists with in total 62 aspects. This Scale is called reliable, valid, sensitive and responsive to change (Birchwood et al. 1990).

c. Cost-effectiveness

Cost-effectiveness: The number and duration of contacts (including the IMR-meetings), crisis contacts, (forced) admissions and duration of admissions are calculated in costs in euro's. These are related with changes in quality of life measured by the EQ-5D (see 8.1.2 c). By transforming scores on the EQ-5D in so called 'Qualy's' cost-effectiveness can be calculated. To calculate cost-effectiveness, only cost of health care consumption is included: no social costs such as rent, benefits, etc. The major costs are the costs associated with hospital admissions.

